2.9 Correlative Studies Background

i. Archival tissue and cell-free plasma DNA to assess genomic alterations:

We will incorporate tissue-based and circulating tumor DNA (ctDNA) approaches to assess prostate cancer pathway changes including AR signaling pathway activation (mRNA) and genomic alterations including DNA repair pathways and will correlate with PSMA heterogeneity on imaging. We will evaluate the association of molecular biomarkers with imaging and treatment response. Mechanisms of resistance will be assessed in a subset of patients enrolled at WCM through integrative genome-wide analysis of pre-treatment and progression tumor biopsies. At the end of this Aim, we will have defined the molecular landscape of CRPC patients enrolled on prospective trials of PSMA-targeted radionuclide therapy and will have identified biomarkers associated with outcome to be evaluated in a larger study to determine whether they are predictive or prognostic.

PC is a clinically and molecularly heterogeneous disease with marked variability in patient outcomes. Defining the genomic alterations in PC has improved classification of tumors: for instance, 50% harbor TMPRSS2-ERG gene fusion, 10% SPOP mutation, and germline or somatic alterations involving DNA repair pathways (eg., BRCA2, ATM, MMR defects) occur in 20% of CRPC. Based on recent data from our group and others, we predict that these genomic alterations may help identify patients most likely to respond to DNA damaging therapy with PSMA-targeted radionuclide therapy. In PC models, ERG expression results in relative resistance to ionizing radiation. Conversely, SPOP mutant prostate cancers and/or those with CHD1 loss show increased

genomic instability, play a role in double strand DNA break repair, and result in increased sensitivity to DNA damage. Germline or somatic alterations involving DNA damage repair genes (such as BRCA2 and ATM) have also been shown to be preferentially sensitive to DNA damaging therapy including PARP inhibitors and platinum chemotherapy. We therefore hypothesize that distinct molecular phenotypes of prostate cancer may have predictable and exploitable differences in sensitivity to DNA damaging agents such as ¹⁷⁷Lu. We and others have also described prostate cancer subtypes based upon AR signaling and neuroendocrine differentiation. We hypothesize that the NEPC / AR low tumors would express low PSMA and respond less well to PSMA-targeted therapy. We will test these hypotheses using tissue and ctDNA collected from our prospective cohorts.

We will evaluate archival tumor tissue (preferentially from metastatic biopsies) with the plan for utilization of our prostate cancer specific targeted platform covering DNA (for mutation and copy number) of 74 genes/regions commonly aberrant in prostate cancer and 42 control genes. Prostate cancer genes including AR, SPOP, CHD1, DNA repair, ERG fusion, and other CRPC-relevant alterations. We will also collect a single-sample of blood for germline analysis of DNA repair defects. In addition, we will collect plasma samples for ctDNA analysis prior to treatment, at 3-months, and at progression using the prostate cancer specific PCF SELECT platform developed in collaboration with others as part of a PCF Challenge Award. The panel is also being used for other prospective therapeutic trials which will allow for cross-comparison of data.

Gene expression of androgen signaling genes and other relevant pathways will be assessed using a custom panel Nanostring platform developed and validated by [name] lab. This panel includes 350 genes including the AR signaling signature genes (n=30), the AR V7 splice variant, neuroendocrine prostate cancer genes, epithelial mesenchymal transition, cell cycle- genes, TMPRSS2-ERG fusion transcript, and control/housekeeper genes. As discussed above, we will describe findings from this exploratory endpoint in each study with the plan to analyze identified biomarkers to determine their association with efficacy and toxicity across studies, in particular at doses found to have efficacy.

ii. CTC Count:

Circulating tumor cell (CTC) counts via the FDA-cleared, standard of care CellSearch platform were demonstrated to be prognostic in men with advanced prostate cancer prior to systemic therapy and a "conversion" from an unfavorable count (≥ 5 CTCs/7.5 mL) was associated with a median similar to those starting with favorable counts, leading to clearance of this particular test by the FDA (109). More recently, the combination of CellSearch CTC enumeration and serum LDH have been demonstrated to have prognostic value, meeting Prentice criteria for survival surrogacy in the setting of abiraterone/prednisone treatment in men with mCRPC previously treated with docetaxel (110)

iii. Immune Assays:

We and others have observed some durable responses following radiolabeled-PSMA therapy. Radiation may lead to an induction of or increase in immune responses to locally expressed antigens, but unlike external beam radiation, PSMA-targeting generally delivers radiation to all sites of disease (by imaging) and therefore observing an abscopal response is not possible. In prostate cancer, humoral immune response has already been documented with immunotherapy. *We hypothesize that prostate cancer is immunogenic following PSMA-targeted radiation, and that the serological repertoire in patients may be useful as a pharmacodynamic, prognostic, or even predictive tool.*

We propose to test the hypothesis that radiolabeled anti-PSMA treatment of advanced prostate tumors leads to induction or increase in immune responses to locally expressed antigens by assessing serological changes pre- and post-treatment. Indeed, one surrogate to test whether these tumors become more immunogenic is to measure naturally occurring antibodies in the serum or plasma of patients. Autologous serotyping, i.e., serum antibody recognizing tumor-derived antigens, have resulted in a growing list of human cancer antigens that are immunogenic in the host of origin. With regard to cancer antigens recognized by the humoral immune system, over 2700 sequences have been identified by SEREX analysis of sera from patients with a wide range of cancers; these antigens include mutational, overexpressed, oncogenic viral, differentiation, and cancer-testis (CT) antigens. These can be rapidly tested in high-throughput ELISA using recombinant antigens (Grand Serology). In some cases, such as the cancer/testis antigen NY-ESO-1, serum antibodies are associated with spontaneous T cell responses measurable from peripheral blood. It should be noted that most of the antigens defined as targets of autoantibodies are intracellular, rather than surface antigens, and reflect the capacity of the immune system to detect abnormalities associated with neoplasia. The prevalent hypothesis is that antibodies are generated as antigens are released from dying tumor cells, either because of spontaneous necrosis or because of external treatments. The presence of antibodies to intracellular targets can be used as a marker of tumor existence or progression, but can also have a functional role to help generating T cell responses through the formation of immune complexes with their cognate antigen. Today, protein microarrays allow for the detection of specific serum antibodies against a very large number of targets simultaneously. Arrays can be used to determine patterns of antigens recognized by autoantibodies during the course of diseases. These tools are also useful to measure changes in antibody responses with treatment such as immunotherapies. The opportunity to define “seromic” changes in these prostate cancers, i.e., the scope of antigens recognized with increased specificity and frequency by post-treatment patient sera vs. baseline, is now within reach, provided adequate analyses of the vast amount of data generated by these microarray can be properly interpreted.

Grand serology: A series of known tumor antigens will be assessed in a hypothesis-driven manner for their capacity to elicit autoantibodies in advanced prostate cancer patients, at baseline and after treatment with PSMA-TRT. Using ELISA as previously described, we propose to test a series of 20-25 tumor antigens, including mutational, stem-cell, endogenous retroviral, and cancer-testis antigens such as TP53, NY-ESO-1, GAG-HERV-K, SOX2, PRAME, WT1, MAGE-A3, SSSX2, CT45, etc., most of which already have demonstrated spontaneous immunogenicity various solid tumors, including advanced prostate cancer. Briefly, sera will be

tested in 4x serial dilutions, starting from 1/100, for IgG reactivity against full-length E. coli- or yeast-produced proteins of tumor and control antigens to assess specificity. Positive and negative control sera with known reactivity will be used on each plate to validate the assays. Reciprocal titers will be extrapolated and considered significant if >100 . In samples with multiple serum collection time points available, significant changes in humoral response will be defined as antigen-specific antibody going from undetectable (titer <100) to detectable (titer >100), or with titers at least 4-fold different between time points. For antigens showing humoral reactivity, mapping of linear epitopes may be assessed using overlapping peptide series covering the sequence of the antigen, to assess polyclonality and potential spreading over time. In a subset of patients, other immunoglobulin isotype or subclass usage may be assessed as well. We propose that systemic tumor antigen-specific antibody responses in plasma or serum may be useful as a marker of immunological response to radiolabeled anti-PSMA treatment in advanced prostate cancer patients, and that increases or induction in immune responses will occur with treatment in comparison to baseline. These experiments are expected to shed light on both mechanisms of action of the drug, including occurrence of antigen spreading, and on potential predictive biomarkers.

Seromics: While Grand Serology offers a high-throughput way to quickly assess changes of antibody specificity in serum or plasma sample to known tumor antigens, it is limited by the small number of tumor targets identified to date, especially in prostate cancer. To circumvent this limitation, an alternative is to use a broader array of self-antigens instead as potential targets of immune responses generated by immunotherapy.

Seromics is an exploratory, non-biased, hypothesis-generating platform that allows the testing of thousands of human proteins simultaneously as potential targets of autoantibodies from patient serum or plasma. The method only requires a few microliters of material, and may be customized for applications other than IgG antibody detection. The seromic platform can be used to define biomarkers or sets of antigens present at baseline in specific patient populations, and that could be used as prognostic or predictive markers. It has been previously described that prostate cancer spontaneously elicits humoral responses to a small subset of autoantigens that are not immunogenic in healthy donors. Accordingly, seromics is suited to comprehensively look for serum antibody changes in prostate cancer patients at the antigen-specific level between consecutive time points, before and after treatment with radiolabeled anti-PSMA therapy. We plan to use either ProtoArrays (Invitrogen) or HuProt (CDI), protein microarrays spotted with 9000 to 20000 cancer- and non-cancer associated proteins and controls, to define serum autoantibody changes in a subset of proposed treated patients (pre-post) with favorable outcomes, and compare them to changes in age-matched patients with no response.

Immunogenic cell death: we hypothesize that the PSMA TRT will lead to generation of an immune response that will induce immunogenic cell death.

High mobility group box 1 (HMGB1) is an important mediator of immunogenic cell death, and it has been shown that it is released by dying tumor cells following radiation. HMGB1 may promote dendritic cell activation and migration and antigen presentation; following certain anti-neoplastic therapy (such as radiation) higher levels of HMGB1 have been associated with improved

outcomes. We will assess HMBG1 via ELISA in serum obtained pre-and post-treatment with PSMA-TRT and analyze for associations with response, progression-free survival, and overall survival outcomes. We have stored serum (previously collected for HAHA assessment) from prior studies with long-term outcome data and continue to prospectively collect serum from patients being enrolled in current PSMA-TRT studies.

Among the several markers of immunogenic cell death, calreticulin is one of the most investigated. Calreticulin exposure on tumor cell surface is widely accepted as an “eat-me” signal, which is required for phagocytosis of dying tumor cells. Mainly an endoplasmic reticulum (ER)-associated chaperone protein, CTR translocation to the plasma membrane is triggered by reactive oxygen species (ROS)-induced ER stress, dictating the immunogenic cell death. We hypothesize that calreticulin tumor cell expression and cellular localization is associated with tumor response to the immunogenic response-inducing PSMA TRT. Unfortunately, the availability of pre- and post-treatment tumor tissue is often a logistical problem in patients with prostate cancer. We expect to have a subset with pre- and post-treatment tumor tissue available and we will assess membrane expression of CRT in that subset.

[REDACTED]

[REDACTED]

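### The exploratory Grand Serology rule counts a rise through titer 100 at any size but a fall through 100 only if it is at least 4-fold, so noise near the cut is tallied mainly as induction

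*Combined protocol and SAP*

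**What the plan says.** The rule is in Section 2.9, part iii (Immune Assays), under Grand serology. Sera are "tested in 4x serial dilutions, starting from 1/100, for IgG reactivity", and the plan adds: "Reciprocal titers will be extrapolated and considered significant if" they exceed 100. On the panel size, "we propose to test a series of 20-25 tumor antigens".

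Where a man has more than one sample, a significant change is defined as "antigen-specific antibody going from undetectable (titer <100) to detectable (titer >100), or with titers at least 4-fold different between time points". This has two limbs:
- **Crossing limb:** from below 100 to above 100. One direction, no minimum fold.
- **Fold limb:** a 4-fold or larger difference. No direction, so falls count as well as rises.

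The stated expectation is that "increases or induction in immune responses will occur with treatment in comparison to baseline". Table 15, footnote m, gives one serum sample before the first treatment and one at the scan/efficacy visit. The immune objective is exploratory (Section 1.3). Section 12.5.2 says only that biomarker data will be analysed within this study and across related ones. It gives no error rate, multiplicity rule or comparison for this assay.

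**The concern.** Because titers are extrapolated, readings just either side of 100 can occur. A move from 95 to 105 (a ratio of 1.11) is a significant change; a move from 105 to 95 is not. If antibodies have not changed, the two moves are equally likely. Counting one and leaving out the other turns balanced noise into an excess of rises, which is the direction hypothesised. It also removes the matching small falls that would show a reader how much noise there is.

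The rule is applied to 20-25 antigens per man in a single-arm study. There is one sample before treatment, so within-man variability cannot be estimated from a repeat baseline. What is at stake is the reading of the immune correlative, here and in any pooling across studies. The dose-limiting toxicity, PSA and secondary endpoint analyses do not use this rule.

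**Working it through.** The documents state no false-call rate for this rule, so there is no figure to reproduce. The direction of the bias follows from the wording; its size needs assumptions.

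**1. The rule applied to pairs of readings**

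| Pre to post | Ratio | Counted? |
|---|---|---|
| 95 to 105 | 1.11 up | Yes (crossing limb) |
| 105 to 95 | 1.11 down | No |
| 50 to 350 | 7 up | Yes (crossing limb) |
| 350 to 50 | 7 down, or 3.5 if 50 is set to 100 | Only if the extrapolated value is used |
| 400 to 95 | 4.2 down, or 4.0 if 95 is set to 100 | Yes (fold limb) |

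The text does not say how fold change is computed when one value is below 100, and a titer of exactly 100 falls in neither class.

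**2. Noise at the cut**

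Let q be the chance that a reading exceeds 100, with the true titer unchanged and the two readings independent. Then P(rise through 100) = (1 − q)q and P(fall through 100) = q(1 − q). At a true titer of 100, q = 0.5 and each is 0.25, whatever the assay error. All of those rises count. Of those falls, the fold limb picks up 0%, 0.9% or 29% for an assumed error SD of 0.25, 0.5 or 1.0 on the log2 scale (extrapolated values used). Far from the cut the problem vanishes: at SD 0.25, a true titer of 50 or below, or 200 or above, gives essentially no crossings.

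**3. Averaged over a range of titers**

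Assumptions: true titer unchanged and uniform on the log scale from 25 to 1600 (−1 to +2 four-fold steps around 100); independent normal error with SD 0.25, 0.35 or 0.5 of a step. These SDs equal 4^0.25 = 1.41-fold, 4^0.35 = 1.62-fold and 4^0.5 = 2.0-fold. Results by simulation, per reactive antigen:

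| Error SD | False rises | False falls, <100 set to 100 | False falls, extrapolated values |
|---|---|---|---|
| 1.4-fold | 4.8% | 0.12% | 0.20% |
| 1.6-fold | 7.6% | 1.15% | 1.87% |
| 2-fold | 12.8% | 4.35% | 6.85% |

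The last column counts a 4-fold fall when at least one of the two values is above 100.

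Share of false changes that are rises = rises / (rises + falls):
- Values below 100 set to 100: 4.8/(4.8 + 0.12) = 98%; 7.6/(7.6 + 1.15) = 87%; 12.8/(12.8 + 4.35) = 75%.
- Extrapolated values: 4.8/(4.8 + 0.20) = 96%; 7.6/(7.6 + 1.87) = 80%; 12.8/(12.8 + 6.85) = 65%.

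**4. What this means as a count**

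A second assumed model puts a fraction of antigens at true titers of 50-200 and the rest far from the cut. With 25 antigens, 10% near the cut and log2 SD 0.5, the false up-crossing rate is 0.1372 per near antigen. In 27 men (the Phase II maximum, Section 12.2) that is 27 × 25 × 0.10 × 0.1372 = 9.3 false rises through 100, against about 0.14 counted falls through 100. The chance that a man has at least one is 1 − (1 − 0.10 × 0.1372)^25 = 29%. Across 20-25 antigens, 5-25% near the cut and SD 0.25-1.0, that chance runs from 6.9% to 73.3%.

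**5. Mirror-image rule, same model as step 3**

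If any fall through 100 also counts, false falls become 4.8%, 7.6% and 12.8%, equal to false rises. This needs no particular SD or titer distribution: with no true change the pre and post readings are exchangeable, so any rule that treats them as mirror images gives equal rates.

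**The case against.** The strongest reply has four parts.

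- **Falls are counted.** A reader might infer that falls through 100 never count. The fold limb counts any fall of at least 4-fold, including one through 100. This stands, and the working includes those falls.
- **The size is assumed.** A reader might infer that noise alone will show induction in a large share of men. The documents give neither the assay error nor the share of antigens near 100, and antigens well away from the cut contribute almost nothing. This stands: the percentages illustrate, they do not predict.
- **No endpoint is built on the rule.** A reader might infer that the immune objective will be settled by counting men with any change. The plan defines a change for an antigen and sets no per-man endpoint, test or threshold. The objective also draws on seromics, HMGB1 and calreticulin. This too stands.
- **Controls are planned.** Control antigens are used, and positive and negative control sera go on each plate. They check specificity and plate validity; they do not measure how far one man's pre and post readings differ without a true change. The lab manual and the cited ELISA method are not in the documents, so replicates or same-plate pairing may already be in place. Either would reduce noise, but neither would make the rule symmetric.

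Counting falls under the fold limb is not itself an error, since the text defines changes rather than increases.

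**Conclusion.** The point holds as an asymmetry in the definition. Near titer 100, a rise of any size is a significant change, while a fall must be at least 4-fold. Under no true change this tilts the tally towards the hypothesised direction, and the single pre/post pair and the planned controls do not correct it. In the assumed model of step 3, about 65-98% of false changes are rises. That range rests on unchanged titers spread over 25-1600, independent errors of 1.4- to 2-fold, and the two ways of handling values below 100.

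The documents do not support saying that reverse crossings are ignored altogether, or that noise will produce induction at a known rate. The consequence is confined to an exploratory correlative.

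**What to change.** 1. Define loss as the mirror of induction: from above 100 to below 100, or a fall of at least 4-fold. State how fold change is computed when a value is below 100, and where a titer of exactly 100 belongs.
2. Report inductions and losses separately, by antigen and by man.
3. Base any statement about induction on rises against falls within men, for example each man's inductions minus losses, and not on the number of men with any change.
4. As a sensitivity analysis, also require at least a 4-fold change for seroconversion. With values below 100 set to 100, false rises and falls in the step 3 model drop to about 0.1%, 1.2% and 4.4% each. The price is that seroconversion then needs a post-treatment titer of at least 400, so a true 7-fold rise from 50 to 350 would be missed. This is why it should not be the main rule.
5. Where practical, run each man's pre and post sera on the same plate, so that a plate difference does not look like a shift in one direction.

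The mirror rule does not lower the number of false rises; it shows the matching falls, so that the noise can be seen and netted out. The cost is a few lines of wording, some plate layout, slightly more reporting, and a less favourable apparent induction rate. No patient procedure or sample changes.

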- c: Any subject with grade ≥2 neutropenia or thrombocytopenia at Treatment 2 will initially not be eligible to receive the second ¹⁷⁷Lu-J591 / ¹⁷⁷Lu-PSMA-617 infusions. The dose will be held until the toxicity has resolved to grade 1 for a maximum of 2 weeks. If the toxicity has not resolved after 2 weeks, the dose will be discontinued.
- d: CMP (with direct bilirubin in subjects with known Gilbert’s syndrome)
- e: CTC enumeration via CellSearch methodology may be obtained during screening or prior to treatment C1D1
- f: CTC collection for research purposes may be performed during screening or prior to treatment C1D1: two 2.3% sodium citrate “light blue top” tubes
- g: Cell-Free DNA BCT[®] may be obtained during screening or prior to treatment C1D1 and will be whole blood collection in a tube intended for collection, stabilization and transportation of cell-free plasma DNA. 10 mL tube will be used for collecting whole blood for research purposes
- h: Radiographic evaluation will include bone scan, CT/MRI of abdomen/pelvis, and Chest x-ray (CXR waived if CT/MRI includes chest). Following mandatory repeat imaging with Scan/Efficacy visit, continued repeat imaging is recommended approximately 12 weeks until radiographic progression as part of standard care.
- i: Planar/SPECT imaging one week after the ¹⁷⁷Lu-PSMA-617 1st dose infusion in all subjects. Optional imaging will be performed on consenting subjects between D1-D4 and/or prior to treatment #2 on D15.
- j: Survival assessment and relevant medical history to be collected until death
- k: Short-term follow up to be completed q4 weeks following the scan visit until 6 months from the 1st treatment visit. Subjects who are progression-free at 6 months will continue with q4-week labs and q12-week standard imaging per guidelines (as in h above).
- l: PRO = patient reported outcomes = BPI-SF and FACT-P; to be performed at time points specified during treatment phase, then q12 weeks (at imaging time points) during short-term follow up until radiographic progression
- m: serum for immune assays; 1 sample to be collected at any time during screening prior to treatment #1, then again during scan/efficacy visit

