- PSA (Follow up visits 2 & 4)
- LDH (Follow up visits 2 & 4)
- Adverse event evaluation
- Concomitant medications

6.1.2.3 Follow-up lab visits: Follow up Visit 3 (Day 43 \pm 3); Follow up Visit 5 (Day 71 \pm 3)

- CBC with differential and platelet count
- CMP (with direct bilirubin with known Gilbert's syndrome)
- PSA
- LDH

Lab visits may be performed at any CLIA certified lab

6.1.3. Efficacy Evaluation (scan) Visit (Day 85 ± 7; note that these study procedures are not expected to occur on a single day)

The following procedures must be completed during the efficacy visit(s):

- Targeted Physical Examination with vital signs and weight
- Medical History
- Brief Pain Inventory, FACT-P
- ECOG Performance Status
- CBC with differential and platelet count
- CMP (with direct bilirubin with known Gilbert's syndrome)
- PSA
- LDH
- Testosterone
- CTC count via CellSearch methodology
- CTC for research
- Cell-Free DNA BCT[®] Research blood sample
- Immune research blood sample
- Same standard radiographic imaging modality as baseline (CT/MRI and bone scan +/- CXR)
- Single intravenous dose of ⁶⁸Ga-PSMA-HBED-CC (5±2mCi or 185±74MBq)
- PET/CT scan will be obtained between 1 and 3 hours post-injection of ⁶⁸Ga-PSMA-HBED-CC
- Adverse event evaluation
- Concomitant medications
- Concomitant procedures

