9. CORRELATIVE/SPECIAL STUDIES

9.1 Laboratory Correlative Studies

9.1.1 CTC immune analysis:

Whole blood samples (2.7 mL in each vial) in two 4.5 mL 2.3% sodium citrate tubes (light blue top tube) will be collected for research analysis at specified time points (Screening/baseline and efficacy visit). These samples are collected for research purposes only and will not be billed to the subject. CTC will be stained for calreticulin analyzed for research purposes only.

9.1.2 Cell-Free Plasma DNA:

Peripheral blood will be collected in two 10 mL Cell-Free DNA BCT[®] tubes (Streck) at the specified time points (screening or pre-treatment and efficacy visit). These samples are collected for research purposes only and will not be billed to the subject. The cell-free plasma DNA will be analyzed for genomic studies and to identify DNA repair and AR-pathway alterations.

9.1.3 Immune Assay:

Serum samples will be obtained during screening prior to treatment and at the main efficacy visit for immune biomarkers and processed as per the lab manual. Results of these assays will not be billed to the patient and are for research purposes only.

9.1.4 Archival tissue:

Archival tissue will be requested during the screening visit. Fifteen unstained slides containing tumor material from archival paraffin-embedded tissue should be obtained. If available, metastatic tissue is preferred to prostate biopsy/prostatectomy specimens. The tissue will be analyzed for PSMA expression and DNA damage repair pathways for research purposes only.

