10.7 Time to PSA Progression

Time to PSA progression is defined as the interval between initiating treatment until the PSA rises 25% above nadir provided that the increase is at least 2 ng/mL.

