Median bPFS, rPFS, and OS, including survival curves, will be estimated using Kaplan-Meier methodology. Greenwood's formula will be used to calculate 95% confidence intervals for the Kaplan-Meier estimates. Percent change in PSA from baseline will be described by mean/median and standard deviation/inter-quartile range, as appropriate, depending on the distribution of percent change from baseline. Modified RECIST response (i.e., CR, PR, and CR/PR proportions), CTC count response proportion, defined favorable LDH/CTC proportion, and associated 95% confidence intervals, will be estimated via binomial proportions.

All subjects will be offered optional but recommended baseline and subsequent ⁶⁸Ga-PSMA-HBED-CC PET/CT, and those treated with ¹⁷⁷Lu-labeled products will undergo Planar/SPECT imaging. We will analyze the data for associations with response to treatment as well as survival by chi-square tests/Fisher's exact tests and log-rank tests, respectively. For pre/post imaging comparisons, McNemar's chi-square test and paired t-tests/Wilcoxon signed-rank tests will be used, as appropriate. We plan to report data for each individual study as well as across the studies.

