10.9 Calreticulin Expression on CTCs (immune measure)

We will analyze for associations between calreticulin expression as a categorical variable (membrane vs cytoplasmic vs mixed vs no expression) and response to treatment and survival using chi-square tests/Fisher's exact tests and log-rank tests, respectively. We plan to report data for each individual study as well as across PSMA studies.

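### Markers measured at Day 85 are to be related to PFS and survival without a landmark; this matters mainly for biochemical PFS in exploratory analyses and is a minor point

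*Combined protocol and SAP*

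**What the plan says.** **Markers and outcomes.** Section 2.9 (iii, Immune Assays) says that HMGB1 will be measured "in serum obtained pre-and post-treatment with PSMA-TRT and analyze for associations with response, progression-free survival, and overall survival outcomes". No test is named there. Section 10.8 (Analysis of Efficacy) introduces baseline and later PSMA PET together with the planar/SPECT images, then states: "We will analyze the data for associations with response to treatment as well as survival by" chi-square or Fisher tests for response and log-rank tests for survival. Section 10.9 does the same for calreticulin on CTCs ("and response to treatment and survival using chi-square" or Fisher tests and log-rank tests) and names no sampling time.

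**When the markers are measured.** Section 9.1.3: "Serum samples will be obtained during screening prior to treatment and at the main efficacy visit for immune biomarkers". Footnote m of Table 15 agrees: one sample before treatment, "then again during scan/efficacy visit". Table 15 puts the research CTC sample and the repeat PSMA PET at the same two points. Section 6.1.3 dates the visit: "Efficacy Evaluation (scan) Visit (Day 85 ± 7" days.

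**Time zero.** Section 10.7: "Time to PSA progression is defined as the interval between initiating treatment until the PSA rises 25% above nadir". For the other time-to-event endpoints Section 10.8 says only "Median bPFS, rPFS, and OS, including survival curves, will be estimated using Kaplan-Meier methodology". No origin is written for bPFS, rPFS or OS; treatment start is the natural reading.

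**What is absent.** No landmark, time-dependent covariate or rule for men who progress or die before the second sample appears anywhere.

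**The concern.** A value that first exists at about 12 weeks cannot sort patients into groups from Day 1 without using information from the future. Two things can go wrong.

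- A man who progresses in week 6 and is still sampled at Day 85 contributes a marker value that his progression, or a change of therapy after it, may have altered. A test from Day 1 then shows an association that runs from progression to marker.
- A man who progresses early may have no second sample, since progression is a removal criterion in Section 6.4. If he is dropped, every curve starts with a guaranteed event-free stretch. If he is counted as marker-negative, the marker-positive group gains time in which it could not have had an event.

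The results are meant to be used beyond this trial. Section 2.9 suggests that the serological findings might serve as a pharmacodynamic, prognostic or even predictive tool, and Sections 10.8, 10.9 and 12.5.2 plan analyses across several PSMA studies. Adding patients does not remove a bias of this kind; it makes it easier to reach significance.

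**Working it through.** The plan gives no expected PFS for this combination and no share of events before Day 85, so there is no stated figure to reproduce. The figures below are assumption-based.

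**1. Can events precede the marker?**
- *Biochemical PFS: yes.* After Day 1, Table 15 schedules PSA at Treatment Visit 2 (Day 15), Follow-up 2 (Day 29) and Follow-up 4 (Day 57); Section 6.1.2.3 adds Days 43 and 71. Section 10.5 requires a rise above 25% and above 2 ng/mL, confirmed at least 2 weeks later, with no exemption for early rises.
- *Radiographic PFS: hardly.* The first scheduled repeat imaging is at the Day 85 visit itself. Only deaths or unscheduled scans come earlier.
- *OS: deaths only.*

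**2. Share of events before the marker.** Inputs: Day 85 is 84 days after Day 1 (77–91 with the window); 84 / 30.4375 = 2.76 months. Section 2.4.1 cites PFS medians of 6.3 months (item g, with OS 12.7 months) and 13.7 months (item e). Both come from other regimens. With an exponential curve, share = 1 − 2^(−t/median).

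| Median | Share before 84 days | Over 77–91 days | Of 27 men |
|---|---|---|---|
| PFS 6.3 months | 1 − 2^(−0.438) = 26.2% | 24.3–28.0% | about 7 |
| PFS 13.7 months | 1 − 2^(−0.201) = 13.0% | 12.0–14.0% | 3–4 |
| OS 12.7 months | 1 − 2^(−0.217) = 14.0% | 12.9–15.1% | about 4 |

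The curve shape matters. Weibull shapes from 0.8 to 2 give 30% down to 12.5% at the 6.3-month median, and 17.5% down to 3% at 13.7 months.

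**3. Effect on a PFS test from Day 1.** Simulated null marker: 27 men, exponential PFS, censoring uniform over 12–36 months, nominal 5% log-rank. The marker is positive in 50% of men event-free at Day 84 and has no effect afterwards. Positivity in earlier progressors is 25% or 10% (lower positivity gives the higher rate), or 50% in the last row.

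| Early progressors | Median 6.3 months | Median 13.7 months |
|---|---|---|
| All sampled, lower positivity | 10–18% | 7–10% |
| Half sampled, lower positivity | 8–10% | 6–7% |
| None sampled | 5–7% | 5–6% |
| Positivity equal (50%) | about 6% | 5–6% |

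The row with none sampled is also the landmark result: subtracting the same 84 days from every remaining time leaves the log-rank test unchanged.

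**4. If unsampled early progressors are counted as marker-negative.** With 24-month follow-up and a null marker, the event-rate ratio is 0.61 at the 6.3-month median and 0.71 at 13.7 months. A landmark brings both to 1.00.

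**5. OS.** Only men alive at Day 85 can be classified, so the shared early stretch drops out of the between-group test. It does not drop out of the medians: at 12.7 months exponential, men alive at Day 85 have a median from Day 1 of 12.7 + 2.76 = 15.5 months.

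**6. Patients left under a Day 85 landmark for PFS.** 27 × (1 − 0.262) = 19.9, about 20 men; 27 × (1 − 0.130) = 23.5, so 23–24 men.

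**The case against.** A fair defence has four parts.

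- **The plan does not clearly specify the faulty test.** PFS is paired with a post-treatment marker only in Section 2.9, a background section that names no test. Log-rank is named only in 10.8 and 10.9, and for survival. This stands, and a reader should not infer that the plan commits to log-rank tests of Day 85 markers against PFS. But Section 2.9 does commit to relating post-treatment HMGB1 to PFS, and no text says how the timing will be handled.
- **The imaging and calreticulin analyses may use early values.** Section 10.8 gives pre/post imaging its own paired tests, and baseline PET or Day 8 SPECT could be what is related to survival. Section 10.9 names no time. This stands in part: the sentence in 10.8 follows directly on a mention of baseline and subsequent PET, so Day 85 values are not excluded.
- **The bias needs particular conditions.** The inflated rates require that early progressors are sampled and that their positivity is much lower. Section 6.4 suggests many may have left. This stands, and it is why the result is a range that begins at nominal.
- **The aims are exploratory.** Section 1.3 lists immune effects and PSMA imaging as exploratory, and Section 2.9 speaks of associations. This stands and sets the priority.

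A reader might also infer that about a quarter of PFS events would precede the marker. That needs the shorter of the two cited medians and an exponential curve; the other median halves it, and scheduled radiographic progression is not affected at all.

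**Conclusion.** The gap is real but minor. Post-treatment HMGB1, CTC calreticulin and repeat PSMA PET exist only from Day 85 ± 7, and the plan relates post-treatment HMGB1 to PFS and OS, and imaging and possibly post-treatment calreticulin to survival, with no landmark.

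The exposure is mainly in biochemical PFS. Roughly 13–26% of events would precede the marker, on the assumption of exponential times and the two background medians. The false-positive rate at 27 men runs from essentially nominal to about 10–18%. The upper end requires a 6.3-month median, sampling of every early progressor, and positivity of 10–25% in them against 50% in the others; the documents state none of these for this trial. For OS the between-group comparison is essentially sound, and only the medians by marker group would be overstated. Treatment start as time zero is explicit only for time to PSA progression and is inferred elsewhere.

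Baseline marker analyses, the DLT/MTD determination and the phase II PSA-decline endpoint are unaffected.

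**What to change.** Add one rule to Sections 10.8 and 10.9, and refer to it from Section 2.9:

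- Baseline markers are analysed with time counted from Day 1.
- Any Day 85 marker, or change from baseline to Day 85, is related to bPFS, rPFS or OS with time counted from the Day 85 visit, among men who were sampled and free of the event in question at that visit. The number excluded, and why, is reported for each endpoint.

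State the time origin for bPFS, rPFS and OS in the same place.

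The cost is wording only: no new visit, sample or patient. The downside is some loss of patients and events from these exploratory analyses. For PFS about 20 of 27 men would remain at a 6.3-month median and 23–24 at 13.7 months, before any further loss from missing samples.
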